9.4.2 Statistical model, hypothesis, and method of analysis

The primary objective of the study is to evaluate superiority of QAW039 150 mg once daily over placebo (with SoC asthma therapy as the background therapy) by testing the following null hypothesis (H_0) versus the alternative hypothesis (H_a):

[figure not shown]
H_0 : There is no difference in the change from baseline in pre-dose FEV1 at week 12 post-baseline for the patients treated with QAW039 150 mg once daily compared with placebo.

H_a : There is a difference in the change from baseline in pre-dose FEV1 at week 12 post-baseline for the patients treated with QAW039 150 mg once daily compared with placebo.

Familywise type I error rate control

The familywise type I error rate will be controlled at the two-sided 5% level across the primary and secondary null hypotheses using the closed testing procedure shown in [Figure 9-1](#) using the graphical method of [Bretz et al 2009](#). In this closed testing procedure, the primary null hypothesis about pre-dose FEV1 acts as a gatekeeper for the secondary null hypotheses.

Figure 9-1 Closed testing procedure for primary and secondary objectives

Vertices with associated weights denote the individual null hypotheses and their local significance levels. Directed edges between the vertices specify how the local significance levels are propagated in case of significant results. ϵ is set to a very small number in practice. Abbreviations: FEV1 (forced expiratory volume in 1 second); AQLQ+12 (asthma quality of life questionnaire for 12 years and older).

Initially, the alpha is assigned to the primary null hypothesis. Once the primary null hypothesis has been rejected, then 98% of the alpha will be distributed equally amongst the secondary null hypotheses of daytime asthma symptoms and total daily SABA use, respectively, and 2% of the alpha will be assigned to the null hypothesis for AQLQ+12. If one of the secondary null hypotheses is rejected, its local significance level will be propagated to the other secondary null hypotheses as illustrated in Figure 9-1.

Statistical model for primary variable

The primary efficacy variable will be analyzed on FAS using an analysis of covariance (ANCOVA) model with factors for treatment group, age group (<18 vs. ≥ 18 years), use or non-use of a second asthma controller medication at study entry, and region, as well as the baseline daytime asthma symptom score, baseline total daily SABA use and baseline pre-dose FEV1 as continuous linear covariates.

The least squares mean (“adjusted mean”) change from baseline for each treatment group, the difference in the least squares mean changes between the two treatment groups (QAW039 150mg – placebo), and the two-sided adjusted 95% confidence interval along with the p-value for the difference will be obtained and combined from the primary analysis model through the multiple imputation approach described in Section 9.4.3. The superiority of QAW039 150 mg once daily to placebo as add on to SoC asthma therapy is established if the two-sided p-value is less than 0.05 and the 95% confidence intervals lie entirely to the right of 0 L.

Summary statistics for the primary variable

Summaries of absolute values and change from baseline in pre-dose FEV1 by treatment group and visit will be presented. Figures will be produced to visually show the mean pre-dose

FEV1 and the mean change from baseline in pre-dose FEV1 by visit over study period for each treatment group.

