4.1 Inclusion criteria

Patients eligible for inclusion in this study must fulfill all of the following criteria:

1. Written informed consent and assent (if applicable) must be obtained within 14 days prior to or at Visit 1 before any assessment is performed including any adjustment to asthma medication.
2. Male and female patients at a minimum age of 12 years (or higher minimum age limit as allowed by health authority and/or independent ethics committee/institutional review board (IEC/IRB) approvals).
3. Patients must have a diagnosis of asthma (according to [GINA 2016](#)) for a period of at least 6 months prior to Visit 1.
4. Patients who have been treated with:
 - Medium dose ICS, or
 - High dose ICS, or
 - Low dose ICS plus long-acting beta agonist (LABA), or
 - Low dose ICS plus leukotriene receptor antagonist (LTRA), or
 - Medium dose ICS plus LABA.

for at least 3 months prior to Visit 1 and the doses have been stable for at least 4 weeks prior to Visit 1.

5. For patients aged ≥ 18 years, FEV₁ of $\leq 85\%$ of the predicted normal value for the patient, after withholding bronchodilators at Visit 1 and Visit 101. For patients aged 12 to < 18 years, FEV₁ of $\leq 90\%$ of the predicted normal value for the patient, after withholding bronchodilators at Visit 1 and Visit 101.

NOTE: Withholding of bronchodilators prior to spirometry:

- Short-acting β_2 -agonists (SABAs) ≥ 6 hours;
 - Long-acting β_2 -agonists (LABAs) given twice daily ≥ 12 hours;
 - LABAs given once daily ≥ 24 hours;
 - Fixed dose combinations (FDC) of LABA and ICS given twice daily ≥ 12 hours; and
 - Fixed dose combinations of LABA and ICS given once daily ≥ 24 hours.
6. Patients must have a daytime asthma symptom score (0 to 6 scale) of ≥ 1 per day during 4 of the last 7 days of the placebo run-in period.
 7. Patients must have a total daily SABA use ≥ 1 puff per day during 4 of the last 7 days of the placebo run-in period.
 8. Demonstrated reversible airway obstruction as determined by the central reader from the spirometry vendor at Visit 1 or Visit 101. Reversibility is defined as an increase of $\geq 12\%$ and ≥ 200 ml in FEV₁ approximately 10 to 15 minutes after administration of 400 mcg of salbutamol/albuterol (or equivalent). Spacer devices are permitted for administration of salbutamol/albuterol (or equivalent) during reversibility testing only. The Investigator or delegate may decide whether or not to use a spacer for the reversibility testing.

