Blood sample for hematology and chemistry (central laboratory)	X			X				X	X		No fasting requirement prior to blood sampling.
Blood sample for RAST/ImmunoCAP test (central laboratory)	X										
Review Visit 1 laboratory results		S									If results for chemistry, hematology, HbA1c, RAST/ImmunoCAP, urine chemistry and urinalysis are missing, obtain a repeat for the missing result.
Parasitic screening	S										Only if required by health authority and/or ethics committee/ institutional review board. Sites should use local laboratories.
Spirometry (centralized)	X							X			
1 st Pre-dose Spirometry (centralized) approximately - 45 min. pre-dose		X		X	X	X	X		X		To be performed approximately 45 min. prior to in-clinic witnessed study drug administration.
2 nd pre-dose Spirometry (centralized) approximately -15 min. pre-dose		X ^ε		X	X	X	X		X		To be performed approximately 15 min. prior to in-clinic witnessed study drug administration.

Period	Screen	Placebo Run-in		Treatment						Follow-up	Notes
Visit Number (Site visits)	1	101	199	201	202	203	204	TD	299	301	Follow-up Visit 301 is only applicable for patients not participating in the safety study.
Treatment Week	-3	-1	0	0	2	4	8	TD	12	16	Visit 199 and Visit 201 occur on the same day.
Treatment Day	-21	-7	1	1	14	28	56		84	112	
											£To be performed prior to reversibility test.
Reversibility test (spirometry after administration of short-acting β -agonist [SABA])	X**	X ^{α,β**}									
¤To be performed prior to in-clinic witnessed study drug administration.
 
£To be performed after the second (-15 min.) pre-dose spirometry (may be performed after 10 AM \pm 1 h).
 
**If reversibility is NOT demonstrated at Visit 1, reversibility will be attempted at Visit 101. If not achieved, then one additional attempt allowed within 4 days following Visit 101.

Review Visit 1 or Visit 101 or the one additional attempt reversibility result from overread			S								
Asthma exacerbation monitoring	X	X	X	X	X	X	X	X	X	X	In case of an asthma exacerbation, the patient should be encouraged by the site to contact it for advice. If necessary, an unscheduled visit to the site may be arranged.
Serious adverse event monitoring	X	X	X	X	X	X	X	X	X	X	
Adverse event monitoring	X	X	X	X	X	X	X	X	X		
Liver event monitoring	X	X	X	X	X	X	X	X	X	X	If applicable, review lab results and clinical events as per Section 7.3 .
Renal event monitoring	X			X				X	X		If applicable, review lab results as per Section 7.4 .

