9.8 Sample size calculation

The primary objective is to demonstrate that QAW039 150 mg is superior to placebo in pre-dose FEV1 following 12 weeks of post-baseline treatment. A difference of 112 mL in pre-dose FEV1 during treatment was assumed, which is similar to the model-averaged effect seen in study QAW039A2206. The standard deviation (SD) of 380 mL and between-visit correlation for pre-dose FEV1 was based on study QAW039A2206 in a similar population. A treatment discontinuation rate of 15% was assumed based on QAW039A2206 and it was assumed that half of the patients discontinuing study treatment would have week 12 FEV1

values. Simulations were used to determine the sample size due to the complex jump-to-reference missing data imputation approach for the primary analysis.

Under the outlined assumptions, a sample size of 650 patients (325 per arm) will be needed to have 90% power to observe a statistically significant difference between QAW039 and placebo at the two-sided 5% significance level in the primary analysis as shown in [Table 9-1](#). The table also shows the sensitivity of the power to deviations from the assumptions.

Table 9-1 Result of power simulations for the primary variable

Treatment effect (mL)	Discontinuation rate	Sample size	Power
112	15%	650	90.3
112	20%	650	85.9
100	15%	650	80.9

Based on 10,000 simulated trials per scenario and 250 multiple imputations for each trial. Simulations were conducted using SAS/STAT® 13.1 software, Version 9.4 of the SAS System for Linux.

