**Table 2-1 Baseline definition of analysis parameters**

Parameter	Baseline assessment	Detail
ACQ-5, AQLQ [REDACTED]	Last assessment prior to the first dose of study drug on Day 1	If the Day 1 assessment is missing the last available assessment (scheduled or unscheduled) taken prior to the first dose of study drug will be used.

Lung function (FEV 1 )	Average of the two FEV 1 assessments taken at 45 minutes and 15 minutes prior to the first dose of study drug on Day 1	Checks will be performed to ensure both values were taken prior to the first dose of study drug. If one of the 45 and 15 min values is missing (or is not confirmed to be pre-dose) then the remaining non-missing value will be taken as the baseline. If both assessments are missing (or are not confirmed to be pre-dose) then the last available FEV 1 measurement (scheduled or unscheduled) prior to Day 1 will be used for baseline.
eDiary data (Daytime asthma symptoms)	Average of the mean daytime asthma symptom score from Visit 101 to Day 1	The baseline score will be calculated as long as there are at least 4 days with non-missing eDiary data. Noted that the morning assessment for Day 1 counts towards the baseline.
eDiary data (Total daily use of SABA)	Average of total daily SABA use from Visit 101 to Day 1	The baseline score will be calculated as long as at least 4 days with non-missing eDiary data. Noted that the morning assessment for Day 1 counts towards the baseline while the evening assessment for Day 1 counts as the treatment period.

Laboratory data (hematology, clinical chemistry, urine analysis)	Last available assessment (scheduled or unscheduled) prior to dosing on Day 1	
Vital signs (pulse rate and systolic & diastolic blood pressures)	Last available assessment (scheduled or unscheduled) prior to dosing on Day 1	
Height and weight	Last available assessment (scheduled or unscheduled) prior to dosing on Day 1	
ECG	Last available assessment (scheduled or unscheduled) prior to dosing on Day 1	

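### The primary model could also adjust for the pre-dose FEV1 measured at Visit 101: a valid, cheap gain in precision whose size rests on correlations the documents do not print

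*Protocol*

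**What the plan says.** Protocol 9.4.2 and SAP 2.5.3.1 specify an ANCOVA with treatment, age group, second-controller use and region as factors. Its continuous covariates are the baseline daytime symptom score plus "baseline total daily SABA use and baseline pre-dose FEV1 as continuous linear covariates". SAP Table 2-1 defines baseline FEV1 as the average of the two "assessments taken at 45 minutes and 15 minutes prior to the first dose of study drug on Day 1".

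Protocol Table 6-1 lists "Pre-dose Spirometry (centralized) approximately - 45 min. pre-dose" and its -15 minute companion, and marks both at Visit 101 (Day -7) as well as at Visit 201. At Visit 101 both readings come before the reversibility test. Inclusion criterion 5 sets an FEV1 ceiling "after withholding bronchodilators at Visit 1 and Visit 101", so nearly every randomized patient should have a Visit 101 value.

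In the efficacy models, an earlier FEV1 is used only when both Day 1 readings are missing; the last earlier measurement then becomes baseline (Protocol 9.4.1, SAP Table 2-1). Visit 101 FEV1 is not a covariate in the ANCOVA, in the MMRM (Protocol 9.4.4, SAP 2.5.5) or in the `Covbytime` list of the imputation code (SAP 6.6.1).

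**The concern.** One clinic day is a noisy measure of a patient's usual FEV1. With a single baseline occasion, part of the stable between-patient variation stays in the residual. A second occasion measured the same way before randomization can remove some of it without biasing the treatment difference.

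FEV1 is the gatekeeper for all three secondary hypotheses, so a smaller standard error on the primary test helps the whole testing sequence. It matters most where the plan's own sensitivity rows are weaker: 85.9% power at 20% discontinuation and 80.9% at a 100 mL effect (Protocol Table 9-1).

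**Working it through.** **Inputs from the documents (Protocol 9.8).** "a sample size of 650 patients (325 per arm) will be needed to have 90% power"; the test is "at the two-sided 5% significance level in the primary analysis as shown in" Table 9-1. "A difference of 112 mL in pre-dose FEV1 during treatment was assumed". Treatment discontinuation is 15%, and half of those patients are assumed to have a Week 12 value. "The standard deviation (SD) of 380 mL and between-visit correlation for pre-dose FEV1 was based on study QAW039A2206 in a similar population". The correlation is not printed. The text also does not say whether 380 mL is the SD of change or a covariate-adjusted residual SD.

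**Reproducing the plan's power.** Suppose every discontinuer carries no treatment difference.
- Standard error: 380 x sqrt(2/325) = 29.81 mL.
- 112 mL, 15% discontinuation: 112 x 0.85 = 95.2; 95.2/29.81 = 3.194; Phi(3.194 - 1.96) = 89.1%, against 90.3% stated.
- 112 mL, 20%: 89.6/29.81 gives 85.2%, against 85.9%.
- 100 mL, 15%: 85/29.81 gives 81.4%, against 80.9%.

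The stated power is approximately reproduced without any second FEV1 covariate.

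**Model for the gain (assumed).** Let FEV1 at a visit be a person mean (SD tau) plus visit noise (variance s2), with a true 12-week change of variance d2. Treat 380 mL as the SD of change, so 2 x s2 + d2 = 0.380^2 = 0.1444. Let c be the noise correlation between Visit 101 and Day 1.
- Day 1 only: residual = d2 + s2 + tau^2 x [1 - tau^2/(tau^2 + s2)].
- Both visits: replace s2 inside the bracket by s2 x (1 + c)/2.
- Power from the plan's 90.3%: Phi(3.259/sqrt(1 - cut) - 1.96), because 1.96 + Phi^-1(0.903) = 3.259.

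Example with tau = 0.6 L, half of the change variance being noise, and c = 0: s2 = 0.0361 and d2 = 0.0722.
- Day 1 only: 0.1083 + 0.36 x (1 - 0.36/0.3961) = 0.1411.
- Both visits: 0.1083 + 0.36 x (1 - 0.36/0.37805) = 0.1255.
- Cut 11.1%; power 93.3%.

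Cut in residual variance at tau = 0.6 L:

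| Noise share of change variance | c = 0 | c = 0.5 | c = 0.8 |
|---|---|---|---|
| 25% | 5.8% | 2.9% | 1.1% |
| 50% | 11.1% | 5.4% | 2.1% |
| 75% | 15.9% | 7.7% | 3.0% |
| 100% | 20.7% | 9.9% | 3.8% |

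Across tau from 0.5 to 0.8 L:
- c = 0: cut about 6-22%, power 91.9-95.9%.
- c = 0.5: cut about 3-11%, power 91.1-93.2%.
- c = 0.8: cut about 1-4%, power 90.6-91.5%.

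**Check directly on correlations.** Write r1 for Visit 101 with Day 1, r2 for Day 1 with Week 12 and r3 for Visit 101 with Week 12. Then cut = (r3 - r1 x r2)^2 / [(1 - r1^2)(1 - r2^2)]. All values below are assumed.
- Equal correlation rho gives rho^2/(1 + rho)^2: 11.1% at 0.5, 19.8% at 0.8, 22.4% at 0.9, with a limit of 25%.
- (0.90, 0.85, 0.82) gives 5.7%; (0.90, 0.85, 0.80) gives 2.3%; (0.90, 0.80, 0.75) gives 1.3%.
- (0.90, 0.85, 0.765) gives 0%, because 0.765 = 0.90 x 0.85.

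**The weaker planning scenarios.** The same formula can start from 85.9% (1.96 + Phi^-1 = 3.036) or 80.9% (2.834). A 6% cut gives 87.9% and 83.2%; a 22% cut gives 93.0% and 89.4%.

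**The case against.** A reader might infer that the plan discards 6-22% of residual variance for no reason. The documents do not support that, on four grounds.

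- **Independence.** The 6% floor needs visit noise to be independent between two visits seven days apart. Readings a week apart can share a good or bad spell that has gone by Week 12, and the gain then shrinks to a few percent. The top end needs all of the change variance to be noise, so that no two patients truly differ in their 12-week change. This stands.
- **Unprinted inputs.** The deciding correlation is not given, and the meaning of 380 mL is not stated. This stands.
- **Selection at Visit 101.** The eligibility ceiling could narrow the covariate's range. Excluding the top 40% at Visit 101 in an illustrative simulation cut the gain from 19.8% to 14.3% (rho 0.8) and from 11.2% to 5.9% (rho 0.5). But the ceiling is on percent predicted and the covariate is in litres. A second simulation applied an 85%-predicted ceiling (assumed mean 75, SD 13; predicted FEV1 3.3 L, SD 0.7) and showed no loss (14.1% before, 14.6% after). The point is unsettled.
- **Not free.** The new covariate needs handling rules and matching changes in three models. With half of the 15% discontinuers imputed at Week 12 (7.5%), the realised gain is also somewhat smaller than the formulas give. This stands.

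In the other direction, the near-zero cases look strained for this schedule. Visit 101 and Day 1 lie about 91 and 84 days before Week 12, so r3 should be only slightly below r2. True first-order decay from 0.90 at 7 days would give 0.90^12 = 0.28 at 84 days, not 0.85. A very small gain is possible, but it needs a short-term correlation well above the long-term one.

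**Conclusion.** The omission is real: a comparable pre-randomization FEV1 is collected at Visit 101 and is not used as a covariate. The planned ANCOVA is nevertheless valid and prespecified, and its stated power is approximately reproduced. It would be wrong to conclude that the primary analysis is biased or the trial underpowered.

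The benefit is extra precision. Under the assumptions above, the cut in residual variance runs from about 1% to 22%, and it can approach zero if correlation decays steeply. Power would move from 90.3% to somewhere between roughly 90.6% and 95.9%. No narrower figure can be defended from the documents, because the between-visit correlation, the noise share, tau and the meaning of 380 mL all have to be assumed. The sponsor can settle the size from the Phase 2 study that it used for the sample size.

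**What to change.** Before unblinding:

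1. Use the Phase 2 between-visit correlations to quantify the gain.
2. Add the Visit 101 pre-dose, pre-bronchodilator FEV1 (mean of the -45 and -15 minute readings) as a further continuous covariate in Protocol 9.4.2 and SAP 2.5.3.1, in the `Covbytime` list of SAP 6.6.1, and in the MMRM of SAP 2.5.5. Keep Day 1 as the baseline for computing change.
3. Give a missing Visit 101 value, or one censored under Protocol 9.4.1, the mean of all randomized patients, as SAP 2.1.1.1 already does for missing baselines.
4. State what the new covariate takes when a patient's Day 1 baseline has itself been filled from Visit 101, since the two covariates would otherwise be the same measurement.

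The cost is one covariate in text and code plus these two rules; no new data are needed. The identical Phase 3 trial should use the same model so that the pooled efficacy analysis (Protocol section 9) stays consistent. If the Phase 2 correlations show a negligible gain, record that and leave the model unchanged.

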9.4.3 Handling of missing values/censoring/discontinuations

Despite all attempts to ensure complete follow-up for all patients, some patients may not be followed for pre-dose FEV1 for the whole planned study duration. Missing data after discontinuation of double-blind study treatment will be imputed using the jump to reference approach (Carpenter et al 2013). Intermittent missing data prior to discontinuation of double-blind study treatment will be imputed under a missing at random assumption.

A large number of imputed datasets will be created, with their number chosen based on computational feasibility, but at least 1,000. Each dataset will be analyzed using the model described in Section 9.4.2 and the results will be combined using Rubin's rule (Barnard and Rubin 1999) for final inference.

The average of the two FEV1 assessments will only be formed after multiple imputations so that if one of the two FEV1 assessments at a visit is missing, the average will be between the one available assessment and a second imputed assessment. In the situation when both FEV1 values at the randomization visit are missing, the values from preceding visits will be used as described in Section 9.4.1. Retrieved data after the discontinuation of study drug (retrieved drop-out) will remain in the analysis without further imputation for all treatment groups.

9.4.4 Supportive analyses

The primary and the secondary analyses will be repeated for the PPS.

The analysis results and the imputed data for different methods for imputing missing data will be compared.

In a sensitivity analysis, data will be analyzed in the same manner as for the primary analysis, but with missing data imputed using pattern mixture approach combining the jump to reference and the randomized-arm missing at random approaches (Carpenter, et al 2013) by distinguishing the following two cases:

1. A continued treatment effect for QAW039 150 mg patients being lost to follow-up for reasons likely to be unrelated to study drug (e.g. lost to follow-up, withdrew consent) will be assumed (randomized-arm missing at random).
2. Same treatment effect as placebo will be imputed for QAW039 150 mg patients that discontinue study drug and are lost to follow-up due to (or following a study drug discontinuation due to) lack of efficacy, adverse events or death (jump to reference).

If feasible, retrieved drop-out will be used to impute missing post-study drug discontinuation data as a sensitivity analysis. While retrieved drop-outs may be a particularly suitable basis for imputing data for non-retrieved drop-outs as it is most close to the ITT principal, this analysis may not be feasible or may require simplification of the imputation model, because observed post-study drug discontinuation data may be sparse.

The primary efficacy variable will also be analyzed using a repeated measurement analysis model in which treatment, age group (<18 vs. ≥18 years), use or non-use of a second asthma controller medication at study entry, region, visit (where FEV1 measurement is taken per

assessment schedule [Table 6-1](#)) and treatment-by-visit interaction will be included as fixed-effect factors, and baseline pre-dose FEV1 value as well as the baseline daytime asthma symptom score, baseline total daily SABA use and visit-by-baseline FEV1 as covariates. A common unstructured covariance matrix among visits for each treatment group will be used. The analysis will be performed based on all available on-treatment data up to week 12 and based on a likelihood method with an assumption of missing at random (MAR) for missing data assuming a hypothetical situation of continued treatment. On-treatment data is defined as all available data collected while patients took the study drug up to the Week 12 visit. The estimated treatment differences for all treatment comparisons will be tabulated along with the associated 95% confidence intervals and two-sided p-values.

In a tipping point analysis it will be explored by how much the imputed continuous missing data for the investigational and the placebo arm would have had to change compared to the imputations in the primary analysis in order to alter the trial conclusions. This will include an exploration of the possibility that patients with missing data from the investigational arm has worse outcomes than patients with missing data from the placebo arm.

In a further rank-based sensitivity analysis for the primary endpoint, patients will be ranked from smallest to largest in the following sequence with high ranks denoting greater efficacy.

1. patients that died
2. patients that withdrew from the trial
3. patients that completed the trial

Within category 3, patients with higher FEV1 change from baseline will be ranked greater than patients with lower change from baseline. Within categories 1 and 2, patients that withdraw from the trial later will get higher ranks than patients that withdraw early. In case patients withdraw at same study day, patients with higher FEV1 change from baseline at the last assessment are assigned a higher rank. In case of ties in the FEV1 values or no available post-baseline assessments of the primary variable, we use midranks. A Wilcoxon rank-sum test stratified by age group (<18 vs. ≥18 years), use or non-use of a second asthma controller medication, and region will be used to analyze the ranked data.

Subgroups

The primary and secondary analyses will also be conducted by subgroup including for key demographic (e.g., age, sex, race, BMI, geographic region) and disease related subgroups (e.g. number of exacerbations in the previous year, use or non-use of a second asthma controller medication, baseline FEV1 tertiles, ACQ tertiles, XXXXXXXXXX).

